The protocol, informed consent form(s), recruitment materials, and all participant materials will be submitted to the Institutional Review Board (IRB) for review and approval. Approval of both the protocol and the consent form must be obtained before any participant is enrolled. Any amendment to the protocol will require review and approval by the IRB before the changes are implemented to the study. In addition, all changes to the consent form will be IRB-approved; a determination will be made regarding whether a new consent needs to be obtained from participants who provided consent, using a previously approved consent form.

1 PROTOCOL SUMMARY

1.1 SYNOPSIS

Title:

The effect of inflammation and damage to lymph node structures on durable protective immunity following yellow fever vaccination

Study Description:

Our hypothesis is that infections other than HIV can cause lymph node (LN) inflammation and collagen damage to the fibroblastic reticular cell network (FRCn), which will lead to CD4 T cell depletion and impaired vaccine responses. This protocol will study yellow fever vaccine (YFV) in two cohorts of people, one from Uganda and the other from Minnesota where we collect lymphoid tissues (LT) and peripheral blood monocytes (PBMCs) before and after vaccination using a new technique to catalog infectious burden of the individual, determine the relationship between IA, Infections, and immune response.

Objectives:

Primary Objective: To determine the relationship between endemic infections, immune activation (IA), T cell zone (TZ) fibrosis with loss of the fibroblastic reticular cell network (FRCn), CD4 and CD8 T cell subsets and the magnitude and durability of neutralizing antibody response to YFV in a cohort shown to have elevated IA, a damaged FRCn, and pan T cell depletion and a cohort that does not.

Endpoints:**Primary Endpoints:**

[figure not shown]
- 1) Peak titer of neutralizing antibody to yellow fever vaccination

Secondary Endpoints:

1. Measures of T cell zone fibrosis (collagen and desmin) in lymphatic tissue
2. Measures of past and present infection (pathseq, molecular analyses of helminth infection, serum antibody studies) in lymphatic tissue
3. Measures of immune activation (Ki67+ and CD69 + cells) in lymphatic tissue
4. Measures of systemic and lymphatic inflammation (plasma cytokines, frequency of TGF β + and TNF+ cells in lymphoid tissues) in lymphatic tissue
5. Histologic analyses of lymphoid tissues for T follicular helper cells, changes in B cell populations, measures of BAFF+ cells, changes to B cell follicles.
6. Size and change to the frequency of yellow fever antigen specific CD4+ T cell population in lymphatic tissues.
7. Changes in CD8 T cell number and function in lymphatic tissues measured with transcriptomic analyses and standard functional assays (stimulation assays).

Study Population:	This study will include two cohorts of healthy adults in Kampala, Uganda and in Minnesota, USA. The cohort in Uganda will be 30 adults (15 men and 15 women) and the cohort in Minnesota will be 16 adults (8 men and 8 women).
Phase:	N/A
Description of Sites/Facilities Enrolling Participants:	Participants in Minnesota will be recruited and enrolled at the University of Minnesota, Minneapolis, MN. Study visits will occur in the University of Minnesota Health Clinical Research Unit.
	Participants in Kampala, Uganda will be recruited and enrolled at the Joint Clinical Research Center.
Description of Study Intervention:	Yellow fever vaccine (YFV) is a live-attenuated virus vaccine. It is administered in a single subcutaneous injection of 0.5mL of reconstituted vaccine.
Study Duration:	60 months
Participant Duration:	18 months

1.2 SCHEMA

1.3 SCHEDULE OF ACTIVITIES (SOA)

Procedures	Screening Day -42 to 1	Baseline Day -35 to 1	Day 1	Day 3 (+/- 1 day)	Day 5 (+/- 1 day)	Day 7 (+/- 1 day)	Day 10 (+/- 1 day)	Day 12 (+/- 1 day)	Day 14 (+/- 1 day)	Day 17 (+/- 1 day)	Week 3 (+/- 1 day)	Week 4 (+/- 3 days)	Week 6 (+/- 3 days)	Week 8 (+/- 3 days)	Week 10 (+/- 3 days)	Week 12 (+/- 3 days)	Month 6 (+/- 14 days)	Month 9 (+/- 7 days)	Month 12 (+/- 7 days)	Month 15 (+/- 7 days)	Final Study Visit Month 18 (+/- 7 days)
Informed consent	X																				
Physical exam (including height and weight)		X																			
Medical history	X	X																			
Urine Collection		X															X		X		X
Stool Collection		X ^{5,6}			X ⁵						X ⁵					X ⁶	X ⁵	X ^{5,6}	X ^{5,6}		
CBCD/Plts	X																				
Chemistry Panel ³	X																				
T Cell Panel	X	X							X												X
PT/PTT	X																				
HIV antibody	X																X		X		X
YF Neutralizing Ab	X		X	X	X	X	X				X			X							X
Luminex		X								X						X			X		X
LN Biopsy	X									X											
YF Vaccine			X																		
Leukapheresis ⁸		X																	X		
PBMC/Plasma Storage	X ¹	X		X	X	X	X	X	X	X ⁴	X	X	X	X	X	X	X	X	X	X	X
Serum or urine pregnancy test ²	X	X			X			X			X	X						X			
COVID-19 screening ⁷	X	X	X	X	X	X	X	X	X	X	X	X	X	X	X	X	X	X	X	X	X
AE Assessment		X	X	X	X	X	X	X	X	X	X	X	X	X	X	X	X	X	X	X	X

1. Plasma to screen for absence of yellow fever antibodies
 2. For females of childbearing potential
 3. Chemistry Panel to include Albumin, ALT, AST, Alk. Phosphate, Bilirubin (total), Calcium, Chloride, CO2, Creatinine, Glucose, Potassium, Protein (total), Sodium, Urea Nitrogen
 4. This blood draw will be 60 cc for research
 5. Samples will go to the [name] lab
 6. Samples will go to the [name] lab
 7. Verbal screening related to symptoms and recent exposures (see SOP for details)
 8. Large volume blood draw (60 cc) will be done if a participant is not eligible for leukapheresis

2 INTRODUCTION

2.1 STUDY RATIONALE

[figure not shown]
Vaccine responses are known to vary geographically. Bacillus Calmette-Guerin (BCG) for tuberculosis (TB) is perhaps the best known example of a vaccine where efficacy rates vary according to geography, with better responses occurring in northern latitudes (1). Rotavirus vaccine is another where sustained, neutralizing antibody titers are achieved after a single dose in the U.S. and Europe but in developing countries protection is absent or short-lived, even after multiple doses (2-4). Polio and cholera, are also associated with poor antibody responses in developing countries (5-11) and it was recently shown that yellow fever vaccine (YFV) was associated with low levels of neutralizing antibodies in Uganda compared to Switzerland with heightened immune activation (IA) in Ugandans found to be an important factor limiting vaccine responses (12).

Reasons for these geographic differences in vaccine response are unknown, but one possible explanation is that local environmental conditions or endemic infections affect immune function. HIV is an obvious example where infection decreases immune function because of loss of CD4 T cells. There are multiple mechanisms that contribute to CD4 T cell loss in HIV infection, however the major one is from virus replication in lymph nodes (LN) causing an inflammatory reaction, mediated by increased expression of TGF β from T-regulatory cells(13), that leads to collagen formation in the parafollicular T cell zone (TZ)(14). This fibrosis replaces the fibroblastic reticular cell network (FRCn), a structure that is vital to normal immune function. Loss of the FRCn leads to depletion of IL-7(15), a cytokine made by the FRCn, and important for T cell homeostasis. As collagen increases, IL-7 levels decrease and T cell apoptosis increases (15, 16). It is unknown if this process of LN fibrosis leading to lower CD4 counts occurs with other infections, however in large population-based studies of HIV negative people in East Africa, the average CD4 T cell count is significantly less than in Northern European populations. In Uganda, the mean CD4 T cell count is 754 cells/mm³ for men and 894 cells/mm³ for women (17) and in Ethiopia the average for the entire population is 667 cells/mm³ but in Denmark it is 1067 cells/mm³ (18). There are similar studies from other parts of the world that show the same trend of higher CD4 T counts the further north or more developed the country (19-21).

Our hypothesis is that infections other than HIV can cause LN inflammation and collagen damage to the FRCn which will lead to CD4 T cell depletion and impaired vaccine responses. This hypothesis is supported by our preliminary data documenting high levels of collagen in the LN TZ of HIV negative Ugandans (compared to the U.S.) with concomitant loss of the FRCn, the magnitude of which correlates to peak yellow fever neutralizing antibody titer after vaccination. We believe that infections common in the developing world (e.g., helminths, TB, Malaria, and Salmonella) can cause LN inflammation that leads to chronic immune activation (IA) and collagen deposition in the FRCn with subsequent loss of T cells, (including T follicular helper cells). The loss of the FRCn impairs humoral responses to vaccination. We propose a direct test of this hypothesis by studying yellow fever vaccine (YFV) in two cohorts of people, one from Uganda and the other from Minnesota where we collect lymphoid tissues (LT) (i.e., lymph node biopsies), and PBMCs before and after vaccination and using a new technique to catalog infectious burden of the individual, determine the relationship between IA, Infections, and immune response. We will build on our previous work and study larger cohorts of people with more frequent collection of samples.

A central question in vaccine research is why vaccine efficacy rates vary with good protection in some parts of the world and poor protection in others. For BCG, there is a clear geographic difference in efficacy with vaccination in northern latitudes achieving greater efficacy rates (1). Our preliminary data suggest one possible explanation is that inflammation from chronic endemic infections damages LN structures that are required for robust immune responses. We have previously demonstrated that HIV replication in LN causes inflammation that directly leads to CD4 T cell depletion by a process of fibrosis replacing the FRCn of the TZ. The FRCn produces IL-7, which is a primary homeostatic mechanism supporting LT CD4 and CD8 T cells but the FRCn is also important for B cell function and follicle formation. Loss of the FRCn directly leads to increased apoptosis of T cells, and all of their subsets (15, 16), decreased B Cell Activating Factor (BAFF), fewer follicles, and decreased responses to vaccination (22). As described below we now have evidence to suggest that other infections may cause LN fibrosis leading to decreased CD4 T cells which, in turn, may limit vaccine responses. This model is described in **Fig.1**. Demonstration that this process occurs with infections beyond HIV and that it limits vaccine efficacy is highly significant and would suggest that alternative vaccine constructs or strategies may be necessary to improve vaccine efficacy rates, especially for infections like HIV, Malaria, and TB where the greatest burden of infection is in the developing world.

Fig. 1: Proposed mechanism for LN inflammation and TZ fibrosis leading to impaired vaccine responses.

2.2 BACKGROUND

We have previously demonstrated an indirect and significant relationship between TZ fibrosis and CD4 T cell loss by a mechanism of FRCn damage (14-16, 23). This finding, along with the observation of lower T cell counts in developing countries (17-21) raised the possibility that infections other than HIV might also cause LN inflammation and fibrosis. To explore this possibility, we studied 3 groups of HIV negative people (**Table 1**). Group 1 included 30 people from Kampala, Uganda (16 women, median CD4 874 cells/ μ l) for assessment of baseline measures of inflammatory cytokines and LN fibrosis. A subset of 20 were then given YFV with follow-up LN biopsy 10-14 days after vaccination, a time-point when germinal center formation is at its peak (24, 25) and we then obtained blood samples over 14 months of follow-up to measure the titer and duration of YF neutralizing antibodies. Group 2 consisted of 10 HIV-negative

people from Minnesota, USA (3 women, median CD4 953 cells/ μ l) who did not receive YFV but where we did have LN samples to analyze TZ architecture concurrently with Group 1. Group 3 consisted of 10 HIV uninfected participants of a study (26) at Emory University in Atlanta, GA (4 women, CD4 unavailable) where they did receive YFV and where plasma samples from baseline before and again 2 weeks after vaccination were available, allowing direct comparison of antibody titers to Group 1. We also used previously published (23) LN collagen data from HIV+ people from the US as positive controls.

Group	Site	N	YFV	Samples	Duration FU
1	Uganda	30	Subset of 20	LN & blood before and after	14 months
2	Minnesota	10	No	LN	1 time-point
3	Emory University	10	Yes	Blood at baseline and 2 weeks after YFV	2 weeks

Table 1: Description of each group, which groups received YFV, and what samples were collected over FU

At baseline (prior to vaccination) HIV-negative Ugandans have elevated levels of immune activation (IA) and inflammation: We measured IL-1 β , IL-4, IL-6, IL-10, IL-17A, IL-21, IL-22, IL-23, IL-13, MIP-1 β , TNF, TGF β , and IP10 in plasma samples from Group 1 (Uganda) and Group 3 (Emory) prior to YFV administration. We observed significantly higher levels of TGF β , IL-6, IL-4 and IL-21 and MIP-1 β in Ugandans ($p < 0.001$, $p = 0.03$, $p = 0.004$, $p = 0.001$, and $p = 0.01$ respectively, **Fig. 2A, B**). There were no other statistically significant differences detected. The increase in TGF β in Ugandans is interesting as it is the pro-inflammatory cytokine we have previously associated with TZ fibrosis (13) and may be an important mechanism for LN fibrosis in this population as well. We used immunohistochemistry (IHC) and quantitative image analysis (QIA) to stain for Ki67+ cells in LN as a measure of IA. Ugandans had significantly greater frequency of Ki67+ cells ($p = 0.0019$, **Fig. 2C-E**). Collectively these data demonstrate increased IA and inflammation in HIV negative Ugandans, especially in LN.

[figure not shown]
[figure not shown]

Fig. 2: Increased IA in HIV negative Ugandans. Increased levels of TGF β (A), IL-6 (B), and Ki67+ cells in LN (C) in Ugandans. LN sections stained with Ki67 from U.S. (D) and Ugandan I.

There is increased collagen and decreased CD4 T cells in HIV negative Ugandan LN. We used trichrome staining and QIA to determine the amount of collagen in the TZ in Groups 1 & 2 (Fig. 3 A,B). In Group 1 the mean area of the TZ with collagen was 12.4% (S.D. 3.4%) whereas in Group 2 it was 4.3% (s.d. 2.9%). The amount of TZ collagen in HIV negative Ugandans was similar to the HIV+ people from Minnesota where the mean amount of TZ fibrosis was 12.9% (s.d. 7.4%). The regression analysis, after log transformation of the percent TZ area, showed a significantly increased amount of TZ collagen in Group 1 compared to Group 2 ($p<0.0001$, Fig. 3C). We measured the size of the CD4 population in Group 1 and found the expected (14) significant inverse correlation between TZ collagen and TZ CD4 T cells ($p=0.0322$, Fig. 3D).

We next measured the FRCn by staining tissues with an antibody against Desmin. In Fig. 4A we show a representative section of the TZ of a LN from the Minnesota group where the Desmin positive TZ area was 22.6% whereas in the Ugandan Group it was 9.5% (range 5.1% - 19.4%, Fig. 4B-C). As expected, there was a direct and significant correlation between the log-transformed area of the TZ that was Desmin positive and the log-transformed size of the TZ CD4 T cell population ($p< 0.0001$, Fig. 4D).

[figure not shown]

[figure not shown]
Fig. 4: The FRCn is depleted in Ugandans. We used QIA to identify TZ Desmin (brown) in HIV negative people in the U.S. (A) and Uganda (B and C) and then used quantitative image analysis to compare the amount of Desmin in the section to the size of the CD4 T cell population in the LN (D) showing the significant and direct relationship.

In summary, people in Uganda have increased IA, inflammation, TZ collagen, damage to the FRCn, and depletion of CD4 T cells. We next gave Group 1 YFV to determine if development of antibodies correlated to any measures of inflammatory damage to the LN.

There were few follicles prior to YFV and no changes in B cell follicles after YFV. We obtained an additional inguinal LN from 20 people in Group 1 and then administered YFV in the thigh opposite the one just biopsied. Ten to fourteen days later we obtained another LN from the same side the vaccine was given. We measured B cell populations, frequency and location of germinal centers, and frequency of Ki67+ cells before and after vaccination. We found few primary or secondary follicles (germinal centers) before vaccination with no significant increase after vaccination. In 63% of participants we saw no follicle formation and in only 3 of the participants did we see an increase in B cell follicles. The mean area of the follicles with B cells prior to vaccination was 25.5% (range 15.7-39.4%) whereas after vaccination it was 24.1% (range 14.0-34.1%, $p=0.34$). There was a significant increase in the frequency of Ki67+ cells ($p=0.002$).

YFV antibody responses were blunted and of short duration. Titers of neutralizing antibodies to YF were measured by plaque reduction assay (PRA). Initially we compared the week 2 samples between Group 1 and Group 3 using a PRA assay with a lower limit of detection of 10 plaque forming units (pfu) and found only a few of the Ugandans had detectable antibodies whereas most of Group 3 had detectable antibodies ($p < 0.0001$, **Fig. 5A**). We point out that we only had access to plasma samples from Group 3

at the 2 time-points (i.e., D0 and W2) and LN biopsies were not done in that study, so our comparative analysis of antibody formation and decay between these two groups is limited. However, as described below there are historical controls that can be used with Group 1 to make relevant comparisons about peak titer and decay rate(12). We next studied the longitudinally collected plasma samples from Group 1 using a PRA assay with a limit of detection of 100 pfu. We switched to a PRA with a higher threshold of detection titer because the lab performing the first analysis was no longer available to us. We did not duplicate the analysis between Group 1 and 3 as there was limited sample available. Peak titer was seen at the week 3 time-point with a 1.3 log range and a median decrease of 0.9 log by week 60 (Fig. 5B).

These response rates and decay characteristics are similar to those reported by Muyanja in a similar group of Ugandans (12) (and personal communication [name], 2017). Given the variable response in antibody formation and the anatomic changes we found in Ugandan LN, we looked for an anatomic correlate of poor vaccine response and found that measures of the FRCn correlated to the peak antibody titer; the more FRCn, the higher the peak titer of antibodies ($p = 0.02$, Fig. 5C).

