3 OBJECTIVES AND ENDPOINTS

OBJECTIVES	ENDPOINTS	JUSTIFICATION FOR ENDPOINTS
Primary		
To determine the relationship between endemic infections, immune activation (IA), T cell zone (TZ) fibrosis with loss of the fibroblastic reticular cell network (FRCn), CD4 and CD8 T cell subsets and the magnitude and durability of neutralizing antibody response to YFV in a cohort shown to have elevated IA,	Peak titer of neutralizing antibody to yellow fever vaccination	The primary analysis endpoint is the peak titer of neutralizing antibody. We believe that there will be significant differences in the peak titer and durability of titers between the two groups.

OBJECTIVES	ENDPOINTS	JUSTIFICATION FOR ENDPOINTS
a damaged FRCn, and pan T cell depletion and a cohort that does not.		
Secondary		
To determine predictors of levels of neutralizing antibodies	
 1. Measures of T cell zone fibrosis (collagen and desmin) 2. Measures of past and present infection (pathseq, molecular analyses of helminth infection and serum antibody studies) 3. Measures of immune activation (Ki67+ and CD69 + cells) 4. Measures of systemic and lymphatic inflammation (plasma cytokines, frequency of TGFβ+ and TNF+ cells in lymphoid tissues). 5. Changes in T cell number and function 	We believe the reason that titers will be different is that inflammation from endemic infections alters the architecture and therefore the function of the lymphatic tissues which results in less antibody being made. With these secondary endpoints we will measure these potential predictors.
Tertiary/Exploratory		
To determine the impact of LN fibrosis on specific T cell populations including T follicular helper cells and antigen specific T cells.	
 1. Histologic analyses of lymphoid tissues for T follicular helper cells and B cells. 2. Size and change to the frequency of yellow fever antigen specific CD4+ T cell population. 	We have shown that lymphatic tissue fibrosis causes depletion of CD4 and CD8 + T cells however we have never examined the impact on highly specific subsets.

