4.2 SCIENTIFIC RATIONALE FOR STUDY DESIGN

Our preliminary data shows that lymph node inflammation and damage to the FRCn correlates to peak titer. We also show data to suggest that there is significantly less LN damage from inflammation in native Minnesotans (not immigrants—we have not studied that). We think the differences are because of exposure to endemic infections. We will therefore use an open-label, non-randomized design to test our hypothesis.

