9 STATISTICAL CONSIDERATIONS

9.1 STATISTICAL HYPOTHESES

- Primary Efficacy Endpoint(s):

Null hypothesis: There is no difference in peak yellow fever antibody titer between individuals from the US and Uganda.

Alternative hypothesis: There is a difference in peak yellow antibody titer.

- Secondary Efficacy Endpoint(s):

Null hypothesis: There is no difference in baseline LN architecture measures (TZ collagen, FRCn, B cell follicles and populations, Tfh cells, and B Cell activating factor) between individuals from the US and Uganda. Alternative hypothesis: There are differences in these measures between the two countries.

Null hypothesis: There is no association between baseline measures of LN architecture and rate of YFV antibody decay. Alternative hypothesis: There are associations between these measures and rate of antibody decay.

Null hypothesis: Principal components of pathseq data are not associated with country of origin.

Alternative hypothesis: Some principal components of pathseq data are be associated with country.

Null hypothesis: There are no difference in helminth infection patterns between the US and Uganda.

Alternative hypothesis: Differences in helminth infections exist between the two countries.

Null hypothesis: Pathseq principal components with strong loadings for infection organisms are not associated with baseline measures of LN architecture. Alternative hypothesis: PC components with strong loadings for infectious organisms are associated with baseline LN architecture measures.

Null hypothesis: Presence of helminth infection is not associated with baseline LN architecture measures. Alternative hypothesis: Presence of helminth infection is associated with baseline LN architecture measures.

Null hypothesis: There is no association between changes in immune function after vaccination and measures of LN architecture. Alternative hypothesis: There is an association between change in immune function and measures of LN architecture.

Null hypothesis: There is no association between CD4, CD8 functional variables and CD4 subsets and peak YFV antibody titers or rate of antibody decay. Alternative hypothesis: There is an

association between CD4, CD8 functional variables and CD4 subsets and peak YFV antibody titers and rate of antibody decay.

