9.4.3 ANALYSIS OF THE SECONDARY ENDPOINT(S)

Differences in rate of YFV antibody titer decay will be compared between vaccinated Ugandans and Minnesotans using linear mixed effects regression model with measurement time, country, and the interaction between measurement time and country as predictors. Baseline LN measures (area with collagen, area with desmin staining, frequency and size of B cell follicles, and frequency of Tfh cells) will be compared between the two countries using Mann-Whitney U tests.

We will examine the association between vaccine response over time and baseline LN measures using linear mixed effects models adjusting for measurement time and gender.

To examine differences in infection patterns between the two countries, we will perform principal component analyses on the baseline pathseq data. We will test for differences in infection patterns between Uganda and the US populations using logistic regression with country as the outcome and the scores for each of the first five principal components as predictors. Differences in helminth infections between Ugandans and Minnesotans will be compared using Fisher's exact test.

We will examine the association between infection history and baseline LN architecture by fitting separate linear regression models for each measure of baseline LN architecture with gender and the 5 pathseq principal component scores as predictors. The association between helminth infections and baseline LN architecture measures will be assessed using Mann-Whitney U tests.

To elucidate the role of previous infections on inflammation and activation we will use sparse canonical correlation analysis (Reference: Witten, D., Tibshirani, R., & Hastie, T. (2009). A penalized matrix decomposition, with applications to sparse principal components and canonical correlation analysis. *Biostatistics*, 10(3), 515-534.) to identify sets of organismal sequences correlated with baseline measures of systemic and lymphatic inflammation (plasma cytokines, frequency of TGF β + and TNF+ cells in lymphoid tissues) and immune activation (Ki67+ and CD69 + cells). The association between helminth infection and measures of inflammation and activation be assessed using a logistic lasso regression model. Measures which have non-zero coefficients in the model will be considered associated with helminth infection.

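### No hypothesis or model relates lymph node architecture to peak titer, and the one lymph node–titer model omits country and the interaction needed to test decay

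*Combined protocol and SAP*

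**What the plan says.** Section 2.2 reports that, among vaccinated Ugandans, "measures of the FRCn correlated to the peak antibody titer; the more FRCn, the higher the peak titer of antibodies" (p = 0.02). Section 4.2 gives this as the reason for the design: "Our preliminary data shows that lymph node inflammation and damage to the FRCn correlates to peak titer". The primary objective in Section 3 covers "the magnitude and durability of neutralizing antibody response to YFV", with FRCn loss among the factors to be related to it. Peak titer is the only primary endpoint. The secondary objective is "To determine predictors of levels of neutralizing antibodies", and collagen and desmin head the list of candidate predictors.

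The analysis sections do not carry this through:

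- **Section 9.4.2** compares peak titer between countries by Mann-Whitney test, stratified by gender. It has no LN term.
- **Section 9.1** gives one hypothesis linking LN architecture to antibody: "There is no association between baseline measures of LN architecture and rate of YFV antibody decay". Peak is not named there, although another hypothesis in the same section names both peak and decay for the CD4 and CD8 variables.
- **Section 9.4.3** gives one matching model: "We will examine the association between vaccine response over time and baseline LN measures using linear mixed effects models". The stated adjustments are measurement time and gender. The baseline LN measures, as listed just before, include desmin and collagen areas.

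**The concern.** The relation that motivates the trial is LN architecture against peak titer. If the plan names no such test, the analysis most readers will look for becomes post hoc, with its outcome definition, covariates and threshold chosen after the data are seen.

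The model that is planned also leaves room for misreading. The two cohorts were chosen because they are expected to differ in both LN damage and titer. In a pooled model without country, any LN measure that differs between the cohorts acts partly as a label for country. A significant coefficient could then be reported as support for the fibrosis mechanism when it adds nothing to the primary country comparison. In addition, the hypothesis stated for LN architecture (decay) and the model supplied for it do not match.

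**Working it through.** **1. The plan's own power figure.** Inputs from Section 9.2: 30 and 16 people, difference 1 log, SD 1 log, two-sided alpha 0.05. Noncentrality = 1/√(1/30 + 1/16) = 3.23. With 43 df the critical value is 2.017 and power is 0.884, consistent with the stated figure of over 85%. This concerns the country comparison only; the plan gives no power for any LN–titer relation.

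**2. What the planned LN model estimates.** With balanced data, the coefficient of a baseline measure in a random-intercept model adjusted for time and gender equals that from regressing each person's mean titer on the measure. It is therefore a titer-level quantity. A simulation with assumed inputs (N = 46, alpha 0.01, visits at Week 3, Week 8 and Month 18, mean decline 0.9 log, measurement error 0.3 log, no cohort difference) gave:

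| True relation | Mixed-model LN effect detected | Direct regression on peak detected |
|---|---|---|
| r = 0.52 with peak, none with decay | 86% | 85% |
| Same, early visits also included | 83% | 85% |
| r = 0.52 with decay, none with peak | about 2% | about 1% |

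So the model responds to magnitude, but is nearly blind to the decay hypothesis it is meant to serve.

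**3. Omitted country.** Inputs: TZ collagen 12.4% (SD 3.4) in Ugandans and 4.3% (SD 2.9) in Minnesotans (Section 2.2); titer gap 1 log, SD 1 (Section 9.2); 30 and 16 people. Collagen is used because Section 2.2 gives its mean and SD in both groups, which it does not do for desmin. Titer was generated from country plus noise, with **no** collagen effect within either country, and regressed on collagen and gender, with and without country (10,000 runs each, alpha 0.01).

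| Assumed collagen distribution | p < 0.01, no country term | p < 0.01, country included |
|---|---|---|
| Normal draws floored at 0.5%, then logged | 34% | 1.2% |
| Normal, untransformed | 39% | 1.0% |
| Lognormal with the same mean and SD | 45% | 1.0% |

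These runs use one titer per person with the full 1 log gap. If the gap in average titer over the modelled visits were only 0.5 log, the lognormal case falls to 9%, still well above 1%.

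**4. Is the missing test feasible?** The correlation is not reported. Assuming a Pearson-type test with all 20 vaccinees, p = 0.02 gives t(18) = 2.552 and r = 2.552/√(2.552² + 18) = 0.516. The Fisher-z 95% interval is tanh(0.570 ± 1.96/√17) = 0.09 to 0.78. Power at alpha 0.01 is approximately Φ(atanh(r)·√(n − 3 − k) − 2.576), with k covariates:

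| Assumed r | N = 46, country and gender (k = 2) | 30 Ugandans (k = 0) |
|---|---|---|
| 0.516 | 86% | 65% |
| 0.40 | 55% | 35% |
| 0.30 | 28% | 17% |

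For r = 0.40 and N = 46, one covariate gives 57%. At N = 46, r is read as the partial correlation after adjustment; the earlier result, being within Uganda, is the nearest available guide.

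**The case against.** The strongest reply is that Section 9.4.3 already regresses titer on baseline desmin and collagen, and that a titer-level coefficient speaks to magnitude. This stands. A reader might infer that LN damage is never related to the size of the response, or that the trial cannot confirm or refute its preliminary finding. The documents support neither reading: step 2 shows similar power for the planned coefficient and a direct peak regression when the LN effect is on level.

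It can also be said that Section 9.4.3 uses time-adjusted mixed models for the CD4 and CD8 variables, whose hypothesis names peak and decay together, so the absence of peak from the LN hypothesis may be a drafting gap. That is possible, but the LN model would still lack a country term and an interaction. Section 9.4.7 allows further demographic factors in the models, but does not name country. The permutation p-values in Section 9.4.1 do not help unless permutation is restricted within country, which is not stated.

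A further temptation is to say that pre-response samples dilute the LN coefficient to a fixed fraction of its effect on peak. The plan does not say which visits enter the model, and any such fraction needs an assumed titer curve, so none is claimed here.

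Finally, r = 0.52 is a back-calculation. Section 2.2 gives neither the test nor the number analysed for that correlation.

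**Conclusion.** The point holds in this form: peak titer against LN architecture is the relation at the centre of the rationale and the primary objective, and the plan specifies no hypothesis or model for it. The one LN–titer model estimates average level rather than peak, does not test the decay hypothesis it accompanies, and is open to confounding by country. On the plan's own figures, that confounding yields p < 0.01 in about 34% to 45% of trials with no within-country effect. This rests on a 1 log country gap carrying through to the modelled titers, and on the collagen distributions seen earlier. The trial still tests magnitude in a general sense; what is missing is a prespecified, country-adjusted estimate on the primary endpoint. The wide interval for the earlier correlation (0.09 to 0.78, under the stated assumptions) is a reason to prespecify its replication.

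**What to change.** - **Section 9.1:** add the null hypothesis of no association between baseline LN architecture and peak YFV titer.
- **Section 9.4.3, peak:** add linear regressions of log peak titer, defined as for the primary endpoint, on log baseline desmin area and, separately, on log collagen area, with country and gender as covariates. Report each slope with its 95% CI, plus the Uganda-only slope as the replication of the preliminary result.
- **Section 9.4.3, decay:** in the mixed model, add country and an LN-by-time interaction, fitted over post-peak visits, and name those visits. The interaction is the test of the decay hypothesis.

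The cost is wording and a few regressions on measurements already planned, with a few more tests at the 0.01 level. Adjusting for country loses some precision, because much of the spread in LN measures lies between cohorts. The Uganda-only slope has moderate power at best, so its confidence interval should carry the interpretation rather than a significance verdict.
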